Expansion into a multi-site protocol: In its first year, the study experienced initial delays as the software necessary for IMT was upgraded to be compatible with newer versions of Windows as well as the VA system. Moreover, even after enrollment began, recruitment of systolic HF patients was more difficult than projected. In response to this challenge, the study will be expanded to multiple sites as well as home based exercise session, each with enhanced recruitment and adherence strategies. This change in study design coincides with [name] plans to transition to the VA Pittsburgh Healthcare System (VAPHS) which will be used to the advantage of the protocol design.

1. [name] will continue as PI of the overall trial as well as site PI at the (VAPHS). Four training arms (Aerobic vs. Strength vs. Combined aerobic-strength, vs. IMT) will be completed at VAPHS, along with pre- and post- skeletal muscle biopsies, bloodwork, DXA and functional assessments. 100 HF patients will be enrolled at that campus, drawing from its robust HF program as well as its extensive HF telehealth database (see recruitment strategies below).
2. The study will also continue at the VABHS where enrollment goals will be 50 HF patients. [name] will assume responsibility as the Boston site PI. Exercise randomization at the VABHS will be limited to aerobic vs. IMT, both to increase efficiencies for the reduced staffing available once [name] and members of his staff have departed for Pittsburgh, and also to ensure adequate enrollment to a RR&D SPIRE-funded 1 I21 RX001423-01A1 substudy (Exercise Training in HF: Structural and Functional Cardiac Remodeling [PI-[name]]) which will explore correlative effects of IMT vs. aerobic training on cardiac remodeling. Also, given [name] role as principal investigator in the ancillary SPIRE study of exercise effects on cardiac remodeling as well as the distinctive skillset required for the echo-based analysis of skeletal muscle perfusion (that is part of the original protocol), both the perfusion and remodeling ultrasound assessments will be studied exclusively at the VABHS. This too is a decision to help maximize local enthusiasm for the protocol, as it becomes a distinctive VABHS goal and responsibility.

Table 4: Outline of protocol (by visit)

Initial Assessment	Visit 1	Informed consent and physical exam, physical functional assessment battery (aerobic, strength, 6MWT, Hand Grip, gait speed, Sit to Stand, and questionnaires)

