	Visit 2 (within one week of visit 1)	Skeletal muscle biopsy; Serology and DXA scan Randomization
	Visit 3 (2-3 days after visit 2) (VABHS only)	Reassessment of biopsy site
Exercise Training	Visits 3/4-38/39	Exercise training sessions (3X/weekly; 60 minutes; 12 weeks)
Post assessment	Visit 39/40-41/43	Post-exercise assessment battery and additional group of assessments completed at visits 1 to 2/3

Table 5: Expansion to a Multi-Site Trial

	Recruitment goals	Exercise arms
VAMC Pittsburgh	100	Aerobic (35), Combined aerobic-strength (30 enrollees), IMT (35 enrollees)
VAMC Boston	50	Aerobic (25 enrollees); IMT (25 enrollees)

Total: 150 HF patients: Aerobic—60; IMT—60; Combined—30;

Study Population

• ***Study Population:*** 150 male and female systolic HF patients with mild-moderate symptoms while on optimal medical therapy will be enrolled. This target will allow for adequate power to address the study objectives even after accounting for a 20% drop-out rate due to attrition and/or suboptimal tissue samples for genetic analysis. Given the expansion to two campuses, and the variation in randomization at each site, the overall proportions of patients enrolled will vary from the original study design but still provide a sound statistical foundation for the anticipated analyses (see statistics section below).

• HF diagnosis will be contingent on a previous hospitalization for HF or physician assessment of HF associated. Each candidate will be examined at the time of enrollment by a cardiologist to ensure that he/she is clinically stable.

• ***Inclusion Criteria:***

- NYHA class II or III for the previous three months despite a minimum of 6 weeks of optimal treatment

- Age \geq 50 years

- Left ventricular EF (LVEF) (by echocardiogram or radionucleotide imaging study within 12 months of enrollment).

- Optimal therapy according to AHA/ACC and HFSA HF guidelines, including treatment with ACEI and beta-blocker therapy (for at least 6 weeks), or have documented reason for variation, including medication intolerance, contraindication, patient preference, or personal physician's judgment.

✓ Patients using aspirin (ASA) will be eligible, but asked to hold the medication for 48 hours prior to biopsy. This technique has previously been used with consistent safety. Patients will also be asked to avoid non-steroidal anti-inflammatory medications (NSAIDs) for 48 hours prior to the biopsy.

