General considerations: The analyses described below are of continuous outcome measures, primarily changes in function outcomes and gene expression and either continuous or categorical predictors. All analyses will be performed as general linear models. Potential confounders of each analysis will be outlined below and a 10% rule for evaluating confounders will be used, namely including a potential confounder if a 10% or greater change is seen in the main predictor effect. In all instances, outcome variables will be evaluated for violation of regression assumptions and transformation of these variables will be considered as a remedy if needed. Analyses will generally be performed with an intent-to-treat approach, with sensitivity analyses performed to assess the role of drop-outs on the results.

This grant examines a complex interplay of exercise regimens, gene expression and functional measures, resulting in a number of hypotheses that require testing. We are cognizant of the role of type I error in this and in interpreting results, focus will be placed on the overall results of these analyses and not on the results of individual tests. Thus, for example, significant relationships among gene expression outcomes and treatment categories as a whole will be considered as support for these hypotheses and isolated significant associations will not be unduly weighted in the interpretation of results.

Randomization will be generated using a SAS program based upon permuted random blocks of variable size to assure approximate balance over time and will be stratified by sex and statin use.

Validation of Study Measurements: At the start of the study, there will be two assessments of physical function battery. Intraclass correlations will be used to determine the relative repeatability of the various components of the battery. This information will be included in all manuscripts using these measures.

- *Aim 1. To assess differences in functional outcomes (peak VO₂, 1RM) relative to the training therapy:*

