a) *Aerobic vs. Strength vs. Aerobic-Strength regimens will be compared to one another b) Inspiratory Training will be compared to Aerobic-Strength:* In this aim, we compare the combined aerobic-strength training regimen to the single-therapy regimens of aerobic training and strength training, as well as the inspiratory training regimen. These comparisons will be made with changes in the functional outcomes (peak VO₂, 1RM) from baseline as the continuous outcome measures in separate models and training regimen as the categorical predictor in a general linear model, with the following factors considered as potential confounder variables: age, sex, and comorbidities. To limit the type I error rate, only the pre-planned comparisons of the combined aerobic-strength training to the other regimens will be considered. In addition, secondary analyses will consider the following aerobic, strength and inspiratory variables as outcome variables in similar analyses to those outlined above: 6MWT, sit-to-stand, and hand grip strength.

- **Aim 2. To assess gene expression and skeletal muscle perfusion in relation to the different training regimens:** In this aim, we examine the change from baseline to post-exercise regimen in the expression of proteolytic (FoxO and Ubiquitin) and anti-proteolysis (IGF-1 and PGC-1 α) genes as predictors of the change in functional outcomes (peak VO₂, 1RM) over the same period. Separate general linear models for each functional outcome will be performed with gene expression changes as the primary predictor and the following variables considered as potential confounders: age, sex, and comorbidities. As above, a 10% rule for introducing confounding variables and the transformation of outcome variables to deal with regression assumption violations will be considered.

Treatment regimens will also be categorized as those with and without direct skeletal muscle stimulation and this categorical variable will be considered as a predictor of a change in the expression of proteolytic and anti-proteolysis genes in general linear models in a similar fashion to that described above. In addition, similar general linear models will be used with changes in skeletal muscle perfusion as a continuous outcome and aerobic and inspiratory training vs. strength-only training as a categorical predictor with similar potential confounders as noted above.

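### Combined training is enrolled only at Pittsburgh and the Aim 1 model has no site term, so combined vs aerobic and combined vs IMT each carry 25/60 of any site difference in change

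*Combined protocol and SAP*

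**What the plan says.** The section on expansion into a multi-site protocol states: "Exercise randomization at the VABHS will be limited to aerobic vs. IMT". Table 5 gives these recruitment goals:

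| Site | Aerobic | Combined | IMT |
|---|---|---|---|
| Pittsburgh | 35 | 30 | 35 |
| Boston | 25 | 0 | 25 |
| Total | 60 | 30 | 60 |

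Sample size/Power repeats the same site-specific randomisation. For Aim 1, the change in peak VO2 or 1RM is modelled on training regimen, "with the following factors considered as potential confounder variables: age, sex, and comorbidities", and "only the pre-planned comparisons of the combined aerobic-strength training to the other regimens will be considered". Under General considerations, adjustment follows a change-in-estimate rule, "including a potential confounder if a 10% or greater change is seen in the main predictor effect", applied to the confounders outlined for each analysis. The same section describes randomisation as stratified by sex and statin use. The wider list under Effects of Confounders does not name site. The Study Population section says the plan remains statistically sound although randomisation varies by site, and refers to the statistics section, which does not take up site.

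**The concern.** A Boston patient cannot be allocated to combined training, so allocation probability depends on site. An analysis that ignores site therefore mixes a randomised comparison within Pittsburgh with a non-randomised comparison of Pittsburgh combined patients against Boston aerobic or IMT patients. Any site difference in mean change is then partly read as a training effect.

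The plan does not state that sites are pooled. That is inferred from arm totals summed across sites and from the absence of any restriction by site.

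Because the outcome is change from baseline, fixed baseline or calibration offsets between sites cancel. What remains are differences in response, delivery or adherence. The text offers one possible source: enrolment had begun in Boston before the change under which "the study will be expanded to multiple sites as well as home based exercise session", so some Boston patients may have trained under different delivery. Their number is not given.

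The comparisons affected are pre-planned Aim 1 comparisons. Aerobic vs IMT, which is balanced by site, is not one of them.

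**Working it through.** **Inputs.** Planned counts from Table 5. SD of change 2.2 mL/kg/min, 20% attrition, two-sided 5% and 80% power from Sample size/Power. After 20% attrition: Pittsburgh aerobic/combined/IMT 28/24/28 and Boston aerobic/IMT 20/20, 120 completers in all. Sample size/Power speaks of 210 patients and four arms but gives no site-by-arm counts, so Table 5 is used.

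**The plan's own figures.** With 40 per group the detectable effect is 0.634 SD by the t-test, against 0.64 stated, so that figure reproduces. The stated 1.26 mL/kg/min corresponds to 48 per group: (1.960 + 0.842) × 2.2 × √(2/48) = 1.258. It does not correspond to 40 per group, where 0.64 × 2.2 = 1.41. A 48 vs 48 comparison is aerobic vs IMT. Combined vs either comparator is 24 vs 48.

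**Share of the site difference.** Let D be the Boston minus Pittsburgh difference in mean change, equal in all arms. Without a site term:

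- expected (aerobic − combined) = true effect + (25/60)D − (0/30)D = true effect + 0.417D
- the same holds for IMT − combined
- aerobic vs IMT carries (25/60 − 25/60)D = 0

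Equal attrition leaves the share unchanged (20/48 = 0.417).

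**Size over an assumed range of D.** The false-positive rates come from a simulation of 40,000 replicates with no arm effect.

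| Assumed D (mL/kg/min) | Bias | Share of 1.26 | Share of 1.55 | False-positive rate, no site term |
|---|---|---|---|---|
| 0.25 | 0.10 | 8% | 7% | 5.2% |
| 0.5 | 0.21 | 17% | 13% | 6.4% |
| 1.0 | 0.42 | 33% | 27% | 10.9% |
| 1.5 | 0.63 | 50% | 40% | 17.7% |

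With a site term the rate is 4.9–5.1% throughout. The 1.55 is the detectable difference for combined vs either comparator, derived next.

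**Precision, combined vs aerobic (same for IMT).**

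- No site term: SE = 2.2 × √(1/24 + 1/48) = 0.550.
- Site term: the within-arm site difference has variance 2.2² / (2 × 28 × 20/48) = 0.207, so SE = √(0.550² + 0.417² × 0.207) = 0.582, a rise of 6%.
- Pittsburgh only: SE = 2.2 × √(1/24 + 1/28) = 0.612.

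Detectable differences at 80% power (noncentral t with 117, 116 and 77 degrees of freedom) are 1.55, 1.64 and 1.74.

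**Non-additive case.** Suppose a 1.0 site difference exists only among aerobic patients.

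- Without a site term the bias is 0.417 for aerobic and 0 for IMT.
- With a site term the estimated site effect averages 0.5, so the biases are 0.417 − 0.417 × 0.5 = 0.208 for aerobic and 0 − 0.208 = −0.208 for IMT.
- The Pittsburgh-only comparison is not affected.

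**The case against.** The strongest objection is that no site difference is documented. The plan cites a 0.6 mL/kg/min change for aerobic training as a whole, so site shifts of 1.0 or 1.5 are 1.7 or 2.5 times that change. At 0.25 to 0.5 the false-positive rate is only about 5–6%. The CPX core lab and the standardised training features also make large differences less likely. This is fair and limits the expected size. It does not supply a reason to leave out a factor on which allocation depends.

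Second, the site term is not better in every circumstance. On mean squared error the unadjusted estimate wins when D is below about √(0.582² − 0.550²)/0.417 = 0.46. In the non-additive case above, the site term introduces a bias in combined vs IMT where there was none. That stands. It is why the Pittsburgh-only analysis is needed alongside, and which of the two should lead is a matter of judgement.

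Third, 1.26 is a poor yardstick for these contrasts. Against 1.55 the shares are somewhat smaller, as the table shows.

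Fourth, 25/60 is exact only for the planned counts. The documents conflict on total size and number of arms, and do not say whether any Boston patient enrolled before the expansion received combined training. If 2 or 5 of the 30 had (assumed counts), the share would be 25/60 − 2/30 = 0.35 or 25/60 − 5/30 = 0.25. No passage places combined training at Boston.

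Finally, a stretch of text just before the statistics section was not in the copy available, so the absence of site handling is judged on the rest. Aim 1's own covariate list is intact and omits site.

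**Conclusion.** The concern holds. As written, two pre-planned Aim 1 comparisons are confounded in part by site, each carrying 41.7% of any difference in mean change between Boston and Pittsburgh. The share rests on the Table 5 goals, equal attrition, pooling of sites, and no absorption of the site difference by age, sex or comorbidities. The bias in mL/kg/min rests on an assumed site difference and is zero if there is none.

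The confounding is partial, because each comparator has 35 planned Pittsburgh patients, and it can be dealt with at analysis. It should be fixed before results are seen, so that the handling of site is not a post hoc choice.

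**What to change.** - Include site as a mandatory fixed factor, exempt from the 10% rule, in the Aim 1 models and in every other between-arm model that uses patients from both sites. In those other models the share may be smaller: if aerobic and combined were grouped against IMT in Aim 2, it would be 25/60 − 25/90 = 14%. The perfusion model is exempt, since "both the perfusion and remodeling ultrasound assessments will be studied exclusively at the VABHS".
- Report combined vs aerobic and combined vs IMT restricted to Pittsburgh patients as a sensitivity analysis, to guard against site differences that vary by arm.
- State that randomisation is stratified by site as well as by sex and statin use, as the site-specific arms already imply.
- Describe how Boston patients enrolled before the expansion were allocated and how they will be analysed.

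The cost is analysis wording and one model term. The detectable difference for the affected comparisons rises from about 1.55 to 1.64 mL/kg/min, and is about 1.74 in the Pittsburgh-only analysis. Allocations already made cannot be changed, only described.

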Secondary analyses will include assessment of the relative impact of changes in skeletal gene expression vs. changes in perfusion dynamics as predictors of changes in function and quality of life as outcomes. Measures of changes from baseline in serum inflammation, cytokines, and adipokines, and effects of muscle histology will be included as covariates in these analyses. General linear models will be used (outlined above).

Sample size/Power: In this study, we plan to recruit 210 individuals and assign them to one of 4 treatment arms, i.e., randomized between aerobic, aerobic strength, and IMT in VAPHS and between aerobic and inspiratory muscle training in Boston. Sample size calculations are based on 20% attrition over the course of the study. In general, a sample size of 40 per group, using a t-test of independent samples as a simplified model, results in an effect size of 0.64 SD units for 80% power, using a two-sided alpha of 5%.

- **Aim 1:** For this aim, we present calculations for detecting differences in peak VO₂. Previous work by Becker (108) shows a $2.1 \text{ mL O}_2 \cdot \text{kg}^{-1} \cdot \text{min}^{-1}$ change in peak VO₂ in a 6 month aerobic-strength training regimen. Similarly, Tyne-Lenne, et al. shows a $1.1 \text{ mL O}_2 \cdot \text{kg}^{-1} \cdot \text{min}^{-1}$ change in a strength-only regimen (109), HF-ACTION (85) shows a $0.6 \text{ mL O}_2 \cdot \text{kg}^{-1} \cdot \text{min}^{-1}$ change in an aerobic regimen and the IMT trial by Dall'Ago et al. (12) shows a $4 \text{ mL O}_2 \cdot \text{kg}^{-1} \cdot \text{min}^{-1}$ change with inspiratory training. Standard deviations [SD] of the change in peak VO₂ over an exercise regimen are not directly available but using interquartile range values from the largest study [HF-ACTION, n=1442], we obtain a SD value of 2.2 for a 3-month intervention. This would correspond to detecting a difference of $1.26 \text{ mL O}_2 \cdot \text{kg}^{-1} \cdot \text{min}^{-1}$ in any comparison with 80% power, assuming a SD=2.2.

- **Aim 2:** In a similar fashion, a simplified comparison of those with gene expression below the median vs. those above the median would be able to detect a difference of $1.26 \text{ mL O}_2 \cdot \text{kg}^{-1} \cdot \text{min}^{-1}$ in peak VO₂ with 80% power. Analyses of combined training groups facilitates capacity to detect smaller differences between groups.

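### The detectable difference of 1.26 mL/kg/min, claimed for any comparison, does not hold for any contrast that Aim 1 permits and Table 5 populates, and the Aim 1 contrast list does not match the arms randomised

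*Combined protocol and SAP*

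**What the plan says.** **Contrasts.** The Aim 1 heading in the statistics section says "Aerobic vs. Strength vs. Aerobic-Strength regimens will be compared to one another" and, separately, "Inspiratory Training will be compared to Aerobic-Strength". The text beneath it gives type I error control as the reason for a restriction: "only the pre-planned comparisons of the combined aerobic-strength training to the other regimens will be considered". Aerobic versus IMT is in neither list. The covariates considered are age, sex and comorbidities. Site is not among them, and it is not a stratification factor under General considerations.

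**Allocation.** The section on expansion to multiple sites states "Exercise randomization at the VABHS will be limited to aerobic vs. IMT". Table 5 places 35 aerobic, 30 combined and 35 IMT patients at Pittsburgh, and 25 aerobic and 25 IMT at Boston: "Total: 150 HF patients: Aerobic—60; IMT—60; Combined—30". It has no strength-only patients.

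**Power.** The Sample size/Power section assumes 20% attrition and says that 40 per group detects 0.64 SD with 80% power at two-sided 5%. It takes an SD of 2.2 for the change in peak VO₂ and states that 1.26 mL/kg/min is detectable "in any comparison with 80% power, assuming a SD=2.2".

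**Conflicting totals.** Sample size/Power and Limitations give 210 patients, where Table 5 gives 150. Sample size/Power refers to four arms but then names three. The multi-site section lists a strength arm at Pittsburgh, and Limitations mentions one.

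**The concern.** A detectable difference claimed for every comparison presupposes similar numbers in every arm. The planned arms are unequal, and the smallest, combined, is one side of every contrast that Aim 1 permits. The power statement would then describe a comparison the plan does not make and overstate those it does make.

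Two related problems affect the same text. The heading calls for aerobic versus strength and the text excludes it. One of the three permitted contrasts, combined versus strength, has no strength patients in Table 5. In addition, the combined arm exists only at Pittsburgh, so Boston patients can enter the combined contrasts only as comparators from another site, and no site term is planned.

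The risk is a null result on a combined contrast being read as if the trial had 80% power for 1.26, when power was between one half and two thirds. A contrast list that cannot be run as written also invites choices after the data are seen.

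**Working it through.** **Inputs.** SD 2.2, two-sided 5%, 80% power and 20% attrition (Sample size/Power); arm sizes (Table 5). Completers are 60 × 0.8 = 48 aerobic, 48 IMT and 30 × 0.8 = 24 combined. By site they are 28, 24 and 28 at Pittsburgh (aerobic, combined, IMT) and 20 and 20 at Boston (aerobic, IMT).

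**Formula.** Detectable difference = (1.960 + 0.842) × 2.2 × √(1/n₁ + 1/n₂). The noncentral t version is given where it differs.

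**Reproducing the plan's figures.**
- 0.64 SD at 40 per group: power 0.82 (normal) or 0.81 (t). This reproduces.
- 1.26 from 40 per group: 2.80 × 2.2 × √(2/40) = 1.38 (t: 1.40), and 0.64 × 2.2 = 1.41. This does not reproduce; power at 1.26 with 40 per group is 73% (t: 72%).
- 1.26 needs 48 per group: 2.80 × 2.2 × √(2/48) = 1.26 (t: 1.27). That equals 60 per arm less 20%.

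**Each contrast under Table 5.**

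| Contrast | Completers | SE in SD units | Detectable difference | Power at 1.26 |
|---|---|---|---|---|
| Aerobic vs IMT (not in Aim 1) | 48 vs 48 | 0.204 | 1.26 (t: 1.27) | 80% (t: 79%) |
| Combined vs aerobic or IMT, sites pooled | 24 vs 48 | 0.250 | 1.54 (t: 1.56) | 63% (t: 62%) |
| Same, with a site term | 24 vs 48, both sites | 0.264 | 1.63 | 58% |
| Same, Pittsburgh only | 24 vs 28 | 0.278 | 1.71 (t: 1.75) | 54% (t: 52%) |
| Combined vs strength | no strength patients | n/a | n/a | n/a |

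The site-term SE comes from the design matrix for the five site-by-arm cells (28, 24, 28; 20, 20) with arm and site as factors: 2.80 × 0.264 × 2.2 = 1.63. The same model gives 0.204 for aerobic versus IMT, so that contrast loses nothing by adjusting for site.

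**Attrition is not the explanation.** With no loss at all, 30 vs 60 gives 1.38 and 30 vs 35 gives 1.53.

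**If the total is 210.** No per-arm numbers are given, so these splits are assumptions, each after 20% attrition:
- Four equal arms (42 each): 1.35, so no contrast reaches 1.26.
- Table 5 ratios (67.2, 67.2, 33.6): 1.06 for aerobic vs IMT; 1.30 for combined contrasts pooled, 1.45 within Pittsburgh.
- Three equal arms (56 each): 1.17, so every contrast meets 1.26.

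**The case against.** **Leaving out aerobic versus IMT can be deliberate.** A reader might infer that Aim 1 contradicts itself on this contrast, or errs by omitting it. The documents do not support that. Heading and text both omit it, the text gives a type I error reason, and testing the combined regimen against each other regimen is a legitimate question. The literal contradiction concerns aerobic versus strength.

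**Boston patients do contribute.** A reader might infer that a third of the patients add almost nothing to Aim 1. As written, with no site term, they enter the aerobic and IMT means and bring the detectable difference from 1.71 down to 1.54. The fair criticism is that this gain relies on comparators from a site with no combined arm. With a site term the figure is 1.63, a gain of about 5% over Pittsburgh alone. Boston patients can also inform Aim 2, and supplying the separately funded aerobic-versus-IMT remodeling substudy is a stated reason for the restriction there.

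**The 1.26 may be generic.** It matches 48 per arm, but the plan does not tie it to aerobic versus IMT and reuses it for the Aim 2 median split. Its origin is inference. Whichever origin is right, it does not follow from 40 per group, and it fails for the combined contrasts under Table 5.

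**The plan's own assumed effects exceed 1.26.** Its cited changes (combined 2.1, aerobic 0.6, IMT 4) imply differences of 2.1 − 0.6 = 1.5 and 4 − 2.1 = 1.9. Power at 1.5 is about 77% pooled, 72% with a site term and 67% within Pittsburgh; at 1.9 it is about 93%, 90% and 86%. So combined versus IMT would be adequately powered on those inputs, and combined versus aerobic would fall somewhat short. This limits the consequence but does not make the stated figure correct.

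**The total is unsettled.** This stands: the results rest on 150 patients. Of the three splits of 210 tried, only three equal arms meets 1.26 for every contrast, and that split departs from the proportions in Table 5.

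**Conclusion.** The power statement is wrong as written. For both contrasts that Aim 1 permits and Table 5 populates, the detectable difference at 80% power is 1.54–1.56 pooled, 1.63 with a site term and 1.71–1.75 within Pittsburgh. Against the claimed 1.26, that is 22% larger at the least (1.54/1.26) and 39% at the most (1.75/1.26). The power paragraph is also inconsistent with its own 40 per group.

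The contrast list needs repair on two counts: heading and text disagree on aerobic versus strength, and combined versus strength has no patients in Table 5.

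These figures assume the Table 5 allocation, 20% attrition spread evenly over arms and sites, and SD 2.2. That aerobic versus IMT is the only contrast reaching 1.26 is likewise conditional on Table 5; it cannot be asserted for 210 patients without per-arm numbers.

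**What to change.** 1. Reconcile 150 versus 210 patients and three versus four arms throughout, then make the Aim 1 heading and text list the same contrasts, all between arms actually randomised. Whether the strength contrasts go depends on how the arm conflict is resolved.
2. State the detectable difference for each contrast from the final allocation and drop the claim that one figure covers them all. Under Table 5 that means 1.26 for aerobic versus IMT and about 1.6 for the combined contrasts with a site term. Correct or remove the 40-per-group basis.
3. Include site in the Aim 1 model, because Boston randomises only aerobic and IMT and its patients are otherwise unadjusted cross-site comparators for the combined arm.

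Recommended, though its absence is not an error: pre-specify aerobic versus IMT, the only contrast randomised at both sites, in Aim 1. If Table 5 stands, it takes the place of the unpopulated combined-versus-strength contrast, so the number stays at three and the type I error rationale is not weakened.

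Cost: wording, one model term and a less favourable stated figure for the combined contrasts. No change to recruitment or data collection follows from this point.
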